**Phase II,
Dosimetry-Guided, Peptide Receptor Radiotherapy (PRRT) with
⁹⁰Y-DOTA-tyr³-Octreotide (⁹⁰Y-DOTATOC) in Children and Adults
with Neuroendocrine and other Somatostatin Receptor Expressing Tumors**

Dosimetry guided PRRT with ⁹⁰Y-DOTATOC

Co-Principal Investigators: [name] and M [name], PhD

Co-Investigators:

[name]
[name]
[name]
[name]
[name]
[name]
[name], MS
[name]
[name]
[name], MD
[name]
[name]
[name], BA
[name]
[name]

Document type: PROTOCOL FOR IND #61,907

Version number: 5

IRB# 201708778

Date: August 19, 2019

Project Goals

Demonstrate safety and efficacy of dosimetry-guided peptide receptor radiotherapy using ⁹⁰Y-DOTA-tyr³-Octreotide in patients with neuroendocrine and other somatostatin receptor expressing tumors.

Monitor all adverse events associated with peptide receptor radiotherapy using ⁹⁰Y-DOTATOC.

Schema

Phase II, Dosimetry-Guided, Peptide Receptor Radiotherapy (PRRT) with ⁹⁰Y-DOTA-tyr³-Octreotide (⁹⁰Y-DOTATOC) in Children and Adults with Neuroendocrine and other Somatostatin Receptor Expressing Tumors						
Screening period		Pathology diagnosis of Neuroendocrine Tumor with slides available High resolution, contrast enhanced CT or MRI within 120 days of Cycle 1 ⁶⁸ Ga-DOTATATE PET/CT within 6 months of Cycle 1 No treatment other than Sandostatin or Lanreotide between CT (MRI) and ⁶⁸ Ga-DOTATATE PET and Cycle 1				
Treatment Cycles and Followup		Imaging and Treatment Schedule		Initial ⁹⁰Y-DOTATOC Dose	Cumulative ⁹⁰Y-DOTATOC Dose	Cumulative Renal Radiation
Cycle 1 Week 1	Day 1	Physical exam with height, weight, vitals, labs, med list, GFR, pregnancy test; QOL questionnaire Start 18 hrs IV/PO fluids				
	Day 2	⁹⁰ Y-DOTATOC + IV amino acids Continue IV/PO fluids for 48 hrs		50 mCi/m ² in children; 120 mCi in adults	120 mCi maximum	
	Day 4	⁹⁰ Y-DOTATOC PET/CT				
Cycle 2 Week 7-9	Day1	Physical exam with height, weight, vitals, labs, med list, GFR, pregnancy test Start 18 hrs IV/PO fluids				
	Day2	⁹⁰ Y-DOTATOC + IV amino acids Continue IV/PO fluids for 48 hrs		Dosimetry determined	270 mCi maximum	
	Day4	⁹⁰ Y-DOTATOC PET/CT				
Cycle 3 Week 13-17	Day 1	Physical exam with height, weight, vitals, labs, list, GFR, pregnancy test Start 18 hrs IV/PO fluids				
	Days 2-3	⁹⁰ Y-DOTATOC + IV amino acids Continue IV/PO fluids for 48 hrs		Dosimetry determined	420 mCi maximum	≤ 23 Gy
FU	3 months after treatment	Physical exam with height, weight, vitals, labs, med list, GFR; QOL questionnaire, CT (MRI)				

Appendix 1: Amendment—Single Time Point Dosimetry

Appendix 2: Data Safety Monitoring Plan

Appendix 3: Data Forms

Appendix 4: QoL Questionnaire

1.0 Background and Rationale

1.1 Somatostatin Receptor Positive Tumors

Neuroendocrine tumors are solid malignant tumors that arise from dispersed neuroendocrine cells found throughout the body. Gastroenteropancreatic neuroendocrine tumors (NETs) can be divided into two groups: Carcinoid tumors that may arise from the lungs, stomach, small bowel or colon and pancreatic neuroendocrine tumors (also known as pancreatic islet cell tumors). The clinical behavior of NETs is extremely variable; some may cause hormone hypersecretion and others may not, the majority of them are slow-growing tumors (well-differentiated NETs), whereas some NETs are highly aggressive (poorly differentiated NETs). The incidence of NETs is increasing, from 1.1/100,000 per year in 1973 to 5.3/100,000 per year in 2004¹. Among NETs, 25% have distant metastases and 25% have regional involvement at the time of initial diagnosis¹. Other tumors that express high levels of somatostatin receptors include neuroblastoma and medulloblastoma²⁻⁴.

The radiological detection and staging of these tumors is challenging and requires a multimodality approach. Somatostatin receptor imaging with In-111 Pentetreotide (OctreoScan) and multiphase CT are the most commonly used modalities although the use of endoscopic ultrasound and MRI is rapidly increasing. Surgery is the only curative option for NETs. However, curative surgery in malignant NET is possible in less than 30% of patients with recurrence identified in the majority of patients as late as 15 years after initial surgery. Treatment with somatostatin analogs, which include the short acting subcutaneous and long acting release (LAR) octreotide as well as long acting lanreotide, are effective in stabilizing NETs and have been recently demonstrated to prolong the time to progression of disease^{5,6}. Chemotherapy is generally not effective in low grade NETs, but it may be helpful in high grade and pancreatic NETs. On the other hand, neuroblastoma and medulloblastoma are initially responsive to chemotherapy, but relapses are common and salvage therapies are not very effective, resulting in <30% overall survival at 5 years⁷⁻⁹.

1.2 Somatostatin Receptor Targeted Imaging

Tumors that express somatostatin receptors can be targeted with radiolabeled somatostatin analogues for imaging and treatment (Figure 1), making theranostics using peptide analogs of somatostatin feasible by labeling with one radionuclide for imaging and the same or a different radionuclide for therapy.

Somatostatin receptor gamma camera imaging with In-111 DTPA-octreotide (OctreoScan) targeting somatostatin receptor 2 (SSTR2), is used routinely for imaging of neuroendocrine tumors with a detection rate >90% for well-differentiated carcinoid tumors and majority of pancreatic NETs, but only a 50% detection rate for insulinomas, which may show a weaker expression of SSTR2¹⁰. Over 90% of neuroblastoma tumors express somatostatin receptors¹¹; they can be imaged with Octreoscan and they respond to ⁹⁰Y-DOTATOC therapy^{12,13}. Medulloblastoma has recently been categorized into four genetic categories, each one of which includes tumors which express somatostatin receptors, but no category is 100% positive for somatostatin receptor expression¹⁴⁻¹⁶. We have also imaged medulloblastoma using Octreoscan¹².

More recently, positron emission tomography (PET) radiopharmaceuticals have been developed that can be labeled with Gallium-68 (Ga-68). Gallium-68 is a generator product with a half-life of 68 min (compared to 67 hours for In-111 in OctreoScan). The parent nuclide of Ga-68 is Germanium-68, which has a half-life of 270.8 days. Ga-68 decays by 89% through positron emission and 11% by electron capture. Another advancement has been the identification of DOTA as a superior chelator compared to DTPA, increasing the stability and receptor targeting of somatostatin analogues¹⁷.

A number of Ga-68 DOTA-conjugated peptides have been introduced, including ⁶⁸Ga-DOTATOC, Ga-68 DOTA⁰-1NaI³-octreotide (⁶⁸Ga-DOTANOC) and Ga-68 DOTA⁰-Tyr³-octreotate (⁶⁸Ga-DOTATATE). All of these radiolabeled peptides bind to sstr2, although DOTANOC also binds to sstr3 and sstr5, and DOTATOC to sstr5¹⁸. The primary advantage of Ga-68 based somatostatin receptor PET imaging over OctreoScan SPECT is the higher imaging resolution and accurate quantification of uptake due to robust attenuation correction. The improved resolution and quantification of uptake obtained with ⁶⁸Ga-DOTATOC PET should provide a more accurate assessment of somatostatin receptor density, which will lead to a more accurate prediction of treatment response to somatostatin analogues. A recent study from Europe comparing ⁶⁸Ga-DOTATOC with Octreoscan found ⁶⁸Ga-DOTATOC to be superior in detection of skeletal and pulmonary involvement of neuroendocrine tumors¹⁹. We have now published a study of the reproducibility of ⁶⁸Ga-DOTATOC PET in our institution.

1.3 ⁶⁸Ga-DOTATOC PET in staging disease for patients with metastatic neuroendocrine tumors.

Given the clinical efficacy of peptide analogs of somatostatin as a diagnostic agent, studies to test if therapeutic radiation could be targeted to tumors in a similar manner was a logical next step. Attempts to utilize In-111 DTPA Octreotide as a therapeutic agent have been minimally effective due to the short range of auger electrons utilized in this therapy. The efficacy of sstr2 targeted treatment was improved with the development of somatostatin analogues labeled with beta emitting radioisotopes.

[figure not shown]

Figure 1: Conceptual representation of targeted molecular imaging and therapy of cancerous tumors. A cell surface receptor is identified that is upregulated in cancerous tumor cell relative to normal surrounding tissue and organs. A peptide vector is developed that binds with high affinity and specificity to the molecular target. A chelator is added to the targeting vector via a molecular linker. The chelator can be used to couple a positron emitter as the reporter signal for PET, or with a beta emitting radionuclide (e.g., ⁹⁰Y) for molecular therapy. To be effective, the high binding affinity of the vector for the target antigen and the stable high specific activity radiometallation must be maintained after placement of the chemical linker.

⁹⁰Yttrium-DOTA complexes are extremely stable; the dissociation constant for this complex is approximately 10⁻²⁵ M. The high stability of the ⁹⁰Y-DOTA chelated complex is a major advantage. Additionally, ⁹⁰Yttrium is a high-energy beta minus particle-emitter with a physical half-life of 64.1 h and a mean range of 5 mm in tissue, permitting effective treatment of tumors with heterogeneous sstr2 expression due to bystander effects. ⁹⁰Yttrium is commercially available in sufficient amounts and in a no-carrier-added form that allows the preparation of a radioligand with high specific activity.

There is now a large clinical experience with ⁹⁰Y-DOTATOC peptide radioreceptor therapy (PRRT) in Europe, primarily in adults with neuroendocrine tumors²⁰. An international Phase II clinical trial then followed and included several trial sites in the United States, notably the University of Iowa; we entered 40 subjects²¹. With its low toxicity profile, the significant improvement in symptoms and quality of life and the lack of effective alternative therapies, PRRT has been suggested as possible first-line therapy in adult patients with neuroendocrine tumors. Recent data have also demonstrated a significant survival benefit with PRRT compared to historical controls in this population²¹. We have now conducted a Phase I trial of ⁹⁰Y-DOTATOC in children and young adults at the University of Iowa, which also shows promise of efficacy of this treatment in pediatric patient population¹³.

[figure not shown]

Figure 2. Chemical identity of ⁹⁰Y- DOTATOC and ⁶⁸Ga-DOTATOC

1.4 Somatostatin Receptor Targeted Therapy

Known as peptide receptor radionuclide therapy (PRRT), this molecularly targeted internal radiation has been utilized in Europe for nearly 20 years. The two main radiopharmaceutical agents are ^{90}Y -DOTATOC and ^{177}Lu -DOTATATE, both targeting sstr2. The response rates are very similar with very few complete responses, 20-30% partial responses, and greater than 50% stable disease among patients who have progressed on other therapies^{22,23}. The time to progression following PRRT, for these patients with progressive metastatic neuroendocrine tumors has been 36-48 months compared to 5-7 months with everolimus or sunitinib^{24,25}.

The normal organ at greatest risk for toxicity with ^{90}Y -DOTATOC is the kidney^{21,23,26,27}. In our previous Phase II trial in adults and our Phase I trial in children, we were able to decrease renal toxicity with amino acid infusion and hydration^{13,21,28}. This trial is designed to utilize dosimetry to maximize radiation dose to tumor while minimizing renal toxicity.

1.5 Study design

This is a Phase 2 peptide receptor radionuclide therapy trial of ^{90}Y -DOTATOC in patients with somatostatin receptor positive tumors. The somatostatin receptor targeting of the therapeutic will be checked with ^{68}Ga -DOTATOC PET-CT imaging prior to therapy. Treatment consists of 3 cycles, 6-8 weeks apart. Cycle 1 dose is fixed with Cycles 2 and 3 doses to be determined by dosimetry-based calculation of renal doses from previous cycles not to exceed 23 Gy for the total renal dose.

^{68}Ga -DOTATOC PET imaging and ^{90}Y -DOTATOC peptide receptor radionuclide therapy (PRRT) are readily available in Europe, but neither radiopharmaceutical is approved for use in the United States. We are presently conducting a safety and efficacy trial of ^{68}Ga -DOTATOC PET in adults and children under IND# 114,398, that to date has included over 220 subjects with no serious adverse events. We have conducted a single institution Phase I trial of ^{90}Y -DOTATOC therapy in children and young adults under IND# 61,907 with no serious adverse events¹³, and we have participated in a Phase II trial of ^{90}Y -DOTATOC PRRT in adults, also with no dose limiting toxicities²¹.

The total radiation dose to kidneys with PRRT using ^{90}Y -DOTATOC is currently limited to ≤ 23 Gy for both children and adults. Several reports, including dosimetry performed on children in our Phase I trial, have suggested that this dose limit can safely be raised to as high as 35 Gy to kidneys when performing individualized dosimetry measurements to guide therapeutic dosing of ^{90}Y -DOTATOC^{26,29,30}. We have considerable expertise in the development of theoretical models for dosimetry³¹, as well as experience in performing dosimetry in individual patients^{13,32}. These studies demonstrated a wide variation in renal dose, both between patients and between cycles in any given individual. In this Phase II therapeutic trial, we therefore propose to perform dosimetry for each patient during the first and second cycles of therapy. The method for performing the dosimetry will take advantage of a positron decay component of Yttrium-90 that will allow quantification of radiation dose using PET imaging to measure rate of ^{90}Y -DOTATOC into kidneys, coupled with semi-quantitative measurement of bremsstrahlung energy using single photon emission tomography (SPECT) to follow the body clearance of ^{90}Y -DOTATOC over 72 hrs after injection of the therapeutic dose.

We are currently conducting an imaging trial at the request of the FDA, to compare the efficacy of ^{68}Ga -DOTATOC PET + a low dose CT with ^{111}In -DTPA-tyr³-Octreotide (Octreoscan) SPECT/CT + a high resolution, contrast enhanced CT (or MRI). There are 3 major advantages of ^{68}Ga -DOTATOC PET/CT over Octreoscan SPECT/CT: 1) lower dose of radiation using Gallium-68 ($T_{1/2}=68$ min) versus Indium-111 ($T_{1/2}=2.8$ day); 2) greater sensitivity of PET compared to SPECT imaging; and 3) ^{68}Ga -DOTATOC PET/CT can be completed in a single, 3-hr visit whereas Octreoscan requires 2 visits over a 24 hr period. We now propose to utilize ^{68}Ga -DOTATOC (or ^{68}Ga -DOTATATE) and ^{90}Y -DOTATOC in a dosimetry-guided theranostics trial for both children and adults with neuroendocrine and other somatostatin receptor positive tumors.

2.0 Project Goals

2.1 Demonstrate safety and efficacy of renal uptake dosimetry-guided peptide receptor radiotherapy (PRRT) using ⁹⁰Y-DOTA-tyr³-Octreotide (⁹⁰Y-DOTATOC) in patients with neuroendocrine and other somatostatin receptor expressing tumors.

2.2 Monitor all adverse events associated with peptide receptor radiotherapy using ⁹⁰Y-DOTATOC.

2.3 Establish ⁶⁸Ga-DOTA-tyr³-Octreotide (⁶⁸Ga-DOTATOC) or ⁶⁸Ga-DOTATATE PET/CT as an accurate technique for diagnosis, staging, treatment targeting, and monitoring response to ⁹⁰Y-DOTATOC therapy.

3.0 Hypotheses

3.1 Hypotheses:

1. We hypothesize that dosimetry-guided, individual dosing of ⁹⁰Y-DOTATOC will provide excellent tumor response.
2. We hypothesize that individual, dosimetry-guided dosing of ⁹⁰Y-DOTATOC will provide maximum safe dose to tumor and minimize renal toxicity while limiting renal radiation dose to ≤ 23 Gy.
3. We hypothesize that ⁶⁸Ga-DOTATOC or ⁶⁸Ga-DOTATATE PET/CT will accurately stage extent of disease at study entry and accurately measure response to therapy at six months following last ⁹⁰Y-DOTATOC treatment.
4. We hypothesize that both quantitative PCR and semi-quantitative immunohistochemical analysis of somatostatin receptor 2 (sstr2) expression on the first diagnostic biopsy of neuroendocrine tumor will positively correlate with standard uptake value (SUV) of that subject's first ⁶⁸Ga-DOTATOC or ⁶⁸Ga-DOTATATE PET scan at study entry.

4.0 Objectives

4.1 Primary Objectives

1. Quantify number of CR, PR, MR, SD and progressions in response to dosimetry-guided PRRT utilizing RECIST 1.1 criteria and ⁶⁸Ga-DOTATOC or ⁶⁸Ga-DOTATATE PET to evaluate efficacy of ⁹⁰Y-DOTATOC therapy in children and adults with neuroendocrine and other somatostatin receptor positive tumors.
2. Monitor renal, hematologic, and clinical toxicities associated with dosimetry-guided ⁹⁰Y-DOTATOC PRRT while maximizing total tumor dose and limiting total renal dose of ⁹⁰Y-DOTATOC to ≤ 23 Gy.

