7.0 Calendar of Tests and Procedures

Calendar of Tests and Procedures									
Test	Base line ⁶	C1D1 ⁷	C1D2	C2 D1	C2D2	C3D1	C3D2	3-4 Month Followup ^{8, 11}	6-9 Month Followup
Physical Exam	X	X		X		X		X	X
Medical history/treatment history	X	X							
Vital signs ¹	X	X	X	X	X	X	X	X	X
Medication list	X	X		X		X		X	X
GFR if indicated ²	X	X		X		X		X ¹²	X
Blood Tests ³	X	X	X ¹⁴	X	X ¹⁴	X	X ¹⁴	X	X
QOL questionnaire	X	X						X ¹³	
Pregnancy Test ⁴	X	X ⁹	X ⁹	X	X ⁹	X	X ⁹		
⁶⁸ Ga-DOTATOC (TATE) PET/CT	X								X
Diagnostic CT or MRI	X							X	X
⁹⁰ Y-DOTATOC Therapy (& Amino Acids)			X		X		X		
Skin assessment ¹⁵			X		X		X		
Dosimetry (blood & imaging)			X		X		X		
Adverse Event Assessment	X ⁵	X	X	X		X		X	X
Fluid diary ¹¹		X	X	X	X	X	X		

1. temp, pulse, respirs, b/p, weight. Height at baseline only. Weight at baseline and Day 1 of each cycle.

2. required for children(<18 years). Required for adults (18 and older) if serum creatinine >1.2mg/dl. If required at baseline for patient, then all subsequent time points require nuclear GFR also.

3. blood tests include: CBC/diff, AST, ALT, creatinine, plus urinalysis at baseline only and T.Bili at baseline only.

4. required for females of child bearing potential only

5. Documentation of baseline symptoms

6. All baseline evaluations within 30 days of first ⁹⁰Y-DOTATOC dose except blood tests need to be within 10 days and ⁶⁸Ga-DOTATOC/TATE PET/CT needs to be within 6 months of first ⁹⁰Y-DOTATOC infusion. The diagnostic scans need to be within 120 days of the first ⁹⁰Y-DOTATOC infusion.

7. events only repeated prior to treatment 1 if they fall outside of the baseline windows noted in footnote 6.

8. Patients who discontinue dosing of ⁹⁰Y-DOTATOC early and who have received at least 1 dose of ⁹⁰Y-DOTATOC are also required to complete follow up appointments per calendar

9. repeat testing can be point of care urine pregnancy test done in Nuclear Medicine.
10. Patients will be instructed to have fluid intake of 1.5 liters Day 1 and 2 liters/day on Days 3 & 4.
11. 3-4 month follow up procedures may be performed by patient's local MD.
12. If GFR is indicated, patients will be required to return to UIHC.
13. If patient does not return to UIHC for F/U, QOL may be mailed or e-mailed to patient.
14. Electrolytes will be drawn during the last hour of amino acid infusion.
15. The skin at the site of the infusion will be assessed by clinic visit or phone at 3-5 days following each infusion of amino acids.

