9.2 Expected Adverse Events Associated with ^{90}Y -DOTA-tyr³-Octreotide (^{90}Y -DOTATOC)

Treatment involves administering a radioactive drug into the bloodstream from where it may attach to any cell (cancerous and healthy) that has somatostatin receptors on its surface and normally comes in contact with somatostatin. Therefore, healthy cells may potentially be killed or damaged by this drug. Healthy cells that contain somatostatin receptors are present in the pancreas, stomach, duodenum, small intestine, large intestine, pituitary, and ovaries. No damage to these organs has been seen in the adults who have taken this drug. Other healthy organs which do not contain somatostatin receptors but which normally come in contact with somatostatin include the bladder.

Kidney exposure is due to the renal clearance of this drug as well as the normal amino acid recirculation mechanism that operates to conserve amino acids and small peptides. The kidney contains somatostatin receptors and also comes in contact with ^{90}Y -DOTATOC as it is being excreted. This means the kidney usually receives the most radiation of any normal tissue in the body. Adult humans who have received ^{90}Y -DOTATOC have experienced some damage to the kidney. Some adults have experienced permanent decrease in kidney function, but no adults have required dialysis. **There is a risk that severe kidney damage could occur which may result in the need for permanent dialysis. Kidney damage may occur as a late effect, months after the last dose of ^{90}Y -DOTATOC.**

Adults and children have been treated with ^{90}Y -DOTATOC. Side effects that were observed include: bowel obstruction, diarrhea, weight loss, reduced red blood cells (anemia), reduced white blood cells (increased chance of infection), and reduced platelets (increased chance of uncontrolled bleeding). These effects depended on the dose of ^{90}Y -DOTATOC and occurred at higher doses tested. Most patients recovered from these effects after stopping ^{90}Y -DOTATOC; however, two patients (of a total of over 2500 patients treated as of 12/31/13) have developed myelodysplastic syndrome.

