10.2 Dose Delay

The time elapsed between the end of week 6 of a Cycle Study Period and Day 1 of the next Cycle Study Period should be ≤ 3 weeks. No further interruption between cycles should occur, except delays mandated by the protocol itself or regulatory requirements as in periods of enrollment locks or data review by health authorities. If a longer interruption does occur, the subject's continuation will be at the discretion of the Principal Investigator; approval will not be unreasonably withheld.

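### No blood count is scheduled mid-cycle or within 30 days after Cycle 3, so the descriptive hematologic toxicity rates of primary objective 2 can be biased low by an unknown amount

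*Combined protocol and SAP*

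**What the plan says.** Section 4.1, item 2, sets the objective: "Monitor renal, hematologic, and clinical toxicities associated with dosimetry-guided" treatment. Section 12.2 analyses it with a table of adverse events by type and grade.

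The calendar in Section 7.0 defines when counts are taken:
- Footnote 3: "blood tests include: CBC/diff, AST, ALT, creatinine, plus urinalysis at baseline only". This row is marked at baseline, Day 1 of each cycle, 3-4 months and 6-9 months. Under footnote 7, Cycle 1 Day 1 is repeated only if baseline has gone out of window.
- The Day 2 marks carry footnote 14: "Electrolytes will be drawn during the last hour of amino acid infusion". They are not counts.
- The samples at 1-4 hours and 48 hours in Section 6.2 are for blood dosimetry.

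On spacing, Section 1.5 says "Treatment consists of 3 cycles, 6-8 weeks apart", and the infusion is on Day 2. Section 10.2 tolerates a longer gap: "The time elapsed between the end of week 6 of a Cycle Study Period and Day 1 of the next Cycle Study Period should be" no more than three weeks.

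On recording, Section 9.1 collects adverse events from consent to 30 days after treatment. After that it reports only serious events at least possibly related to the product. It treats a laboratory value as an adverse event only when the investigator finds it clinically significant. Section 9.1.3 and Appendix II give two other limits: one calendar day after imaging, and 27 days.

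**The concern.** Section 9.2 lists falls in red cells, white cells and platelets as observed, dose-dependent effects of the drug. A table of such events by type and grade is normally read as incidence and worst grade. This schedule cannot supply either, because no count is planned in the six weeks after any infusion.

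The gap is longest after Cycle 3, when cumulative exposure is highest. There, the first scheduled count also comes after Section 9.1 has stopped collecting non-serious events. The clinical-significance rule is a second filter: even a low count that is measured need not reach the table. Both act in the same direction, so marrow safety may look better than it was.

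**Working it through.** **1. The plan's own figure.** Ten half-lives: 10 x 64.1 h / 24 = 26.7 days, rounded up to 27. The stated limit reproduces.

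**2. Days from infusion (Day 2) to the next scheduled count (Day 1 of the next cycle).**
- Cycles 6 weeks apart: 42 - 1 = 41 days.
- Cycles 8 weeks apart: 56 - 1 = 55 days.
- With the delay in Section 10.2: 42 + 21 - 1 = 62 days.
- After Cycle 3, at 3-4 months of about 30 days: 90-120 days.

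Scheduled counts within 30 days after an infusion: none in any of the three cycles.

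**3. Counts against the adverse-event limits.** The first count after Cycle 3 is at least 60 days past the 30-day limit (90 - 30) and 63 days past the 27-day limit (90 - 27). For Cycles 1 and 2 it depends on the reading. If the 30 days run from the last treatment, the Day 1 counts of Cycles 2 and 3 fall inside the window; if from each treatment, they fall outside (41 > 30). The calendar itself marks an adverse-event assessment at both follow-up visits, which does not fit a 30-day limit. Whether a non-serious cytopenia first seen at 3-4 months enters the Section 12.2 table is therefore unsettled.

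**4. Can the loss be sized?** Only by assumption, since the documents give neither onset nor duration. Suppose onset is uniform over days 14-35 (a span of 21 days) and each episode lasts d days. The share still present at a count on day V (V = 35 or later) is the part of the onset span at or after V - d, divided by 21.

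| Duration d | Count on day 41 | Count on day 55 | Count on day 90 or later |
|---|---|---|---|
| 7 days | 1/21 = 5% | 0% | 0% |
| 14 days | 8/21 = 38% | 0% | 0% |
| 21 days | 15/21 = 71% | 1/21 = 5% | 0% |
| 28 days | 100% | 8/21 = 38% | 0% |

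After Cycles 1 and 2 the result runs from 0% to 100% within plausible-looking inputs. The zeros after Cycle 3 follow from assuming that every episode ends before day 90. The table shows that the answer is set by the assumptions; it is not an estimate for this trial. It also counts scheduled draws only.

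**5. Stopping rule.** Section 12.2 stops for non-renal toxicity only if four or more subjects have irreversible Grade 4 events. An irreversible cytopenia is by definition still present at a later count, so missed transient episodes do not enter this rule.

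**The case against.** Several points on the other side stand.

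- A reader might infer that no count is taken between infusions. That is wrong: the Day 1 counts of Cycles 2 and 3 fall between infusions, on the day before the next one. What is absent is a mid-cycle count.
- A reader might take Section 9.2 as showing that cytopenias recover within a cycle. It says "Most patients recovered from these effects after stopping" the drug, and that effects occurred at higher doses. This is recovery after treatment ends, with no nadir timing. A cytopenia that lasts until dosing stops would be seen on Day 1 of Cycle 2 or 3.
- A reader might conclude that all transient cytopenias go unrecorded. Symptomatic cases, serious events and unscheduled local counts can still be captured.
- Objective 2 speaks of monitoring, and Section 12.2 is descriptive. No decision rule depends on the rate of transient cytopenia.
- The patient home-going instructions listed in Appendix III could not be read. Interim local counts there cannot be excluded, although required tests belong in the calendar.
- Adding a draw alone would not cure the problem, because the clinical-significance rule could still keep an asymptomatic low count out of the table.

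These points narrow the concern but leave its core intact: the calendar has no count within about six weeks of any infusion, and recording is filtered in the same direction.

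**Conclusion.** The concern holds in a limited form. The schedule and the recording rules together allow two kinds of event to be absent from the Section 12.2 table: asymptomatic cytopenias that begin and resolve between scheduled counts, and non-serious ones first found at the 3-4 month visit. To that extent the descriptive hematologic rates for primary objective 2 are lower bounds.

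The direction is firm for any such episode; the size is unknown. It is tempting to state what percentage of episodes is recorded, but the documents contain no onset or duration data to support one. Nor do they support reading this as a failure of the irreversible Grade 4 stopping rule, which is largely unaffected.

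The conclusion assumes that the calendar is the complete list of required counts.

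**What to change.** 1. **Section 12.2.** Add a table of worst CTCAE grade per subject and per cycle for neutrophils, white cells, platelets and hemoglobin. Build it from every available CBC: scheduled counts, the 3-4 and 6-9 month visits, and any locally drawn count entered in the study record. Apply neither the clinical-significance rule nor the adverse-event window to it. Cost: one table and entry of local results.
2. **Sections 9.1, 9.1.3 and Appendix II.** Reconcile the 30-day, 27-day and one-day limits with each other and with the calendar's blood tests and adverse-event assessments. State whether the limit runs from each or the last infusion. Cost: text only.
3. **Section 7.0 (preferred addition).** Add one locally drawn CBC with differential mid-cycle after each of Cycles 1 and 2, and one within 30 days after Cycle 3. Take the timing from the count data of the earlier Phase I and II studies. Footnote 11 at present covers only one visit ("3-4 month follow up procedures may be performed by patient's local MD"), so extend it to these draws. Cost: about three routine draws per subject, or 3 x 46 = 138 at the Section 12.1 total and 3 x 64 = 192 at the Section 8.2 total, and a less favourable reported rate. One draw narrows the gap without closing it. Under the onset assumption above, a draw on, say, day 28 would find 7/21 = 33% of 7-day episodes and 14/21 = 67% of 14-day episodes, before adding the next Day 1 count.
4. **If no draw is added.** State with the Section 12.2 results that scheduled counts began about six weeks after infusion (three months after Cycle 3), that nadirs were not sampled, and that the rates are lower bounds on incidence and worst grade. Do not label the table as toxicity unresolved at six weeks, because it will also hold symptomatic and serious events from inside the gap. Cost: a sentence in the report.
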